7.3.3.1 Medical Outcome Short Form (36) Health Survey (SF-36®) – Part A only

SF-36 was collected in Part A only and removed from Part B. The SF-36 measures the impact of disease on overall quality of life and consists of eight subscales (physical function, pain, general and mental health, vitality, social function, physical and emotional health) which can be aggregated to derive a physical-component summary score and a mental-component summary score. Scores are normally determined with the use of norm-based methods which standardize scores based on an assessment of the general U.S. population free of chronic conditions. Composite scores range from 0 to 100, with higher scores indicative of better health. The data will be analyzed at Quality Metrics using their software to derive the 8 subscales and the physical-component summary score and a mental-component summary score.

Raw data from Part A for SF-36 will be listed only.

7.3.3.2 Analysis of mHAQ data - Parts B and C only

SF-36 has been replaced with mHAQ for part B as the team felt that SF-36 would not be evaluable due to the small number of patients in the study.

The modified Health assessment questionnaire (mHAQ) is a patient reported outcome (PRO) which is usually self-administered by the patient. The mHAQ is a modification of the HAQ. It was developed to include questions concerning perceived patient satisfaction regarding the same activities of daily living, along with perceived change in degree of difficulty. The number of activities of daily living was reduced from 20 (HAQ) to 8 (mHAQ).

The eight activities measured by the mHAQ are:

1. dressing and grooming
2. arising
3. eating
4. walking
5. hygiene
6. reach
7. grip
8. common daily activities

Patients are asked to rate these daily activities on a scale ranging from 1 to 4 with:

1. without difficulty
2. with some difficulty
3. with much difficulty

4. unable to do

The mHAQ is calculated as the average of the single scores. To do that the following scoring is applied:

- without difficulty = 0
- with some difficulty = 1
- with much difficulty = 2
- unable to do = 3

Values <0.3 are considered normal.

Summary statistics and graphical displays of overall mHAQ score will be provided. All mHAQ data will be listed by Part and treatment group.

7.3.3.3 Analysis of EQ5D data

EQ5D is collected in Parts A, B and C. EQ5D is a generic, self-completed, and easy-to-use questionnaire which provides a health profile and a global rating of perceived health using a visual analogue scale (VAS). EQ5D has two parts consisting of a self-reported description using a five-dimensional classification (health profile - EQ5D_{profile}), and a self-rated global valuation of perceived health using a visual analogue scale or “thermometer” (perceived health - EQ5D_{vas}) (perfect health = 100; worst possible health = 0). Each of the five dimensions of the EQ5D_{profile} - mobility, self-care, performance of usual activities, pain/discomfort, and anxiety/ depression - is divided into three levels of difficulty: “no problem,” “some problem,” or “extreme problem.” Then a health utility score EQ5D_{utility} can be derived from the five dimensions- by summing the results after a coefficient has been applied (see details below). The EQ5D_{vas} score will be reported as collected. In addition, there is a general question to assess the general state of health.

Data handling

Missing data will be excluded from the above analysis.

The EQ5D utility score EQ5D_{utility} is derived as following. Let 1 corresponds to “no problem,” 2 for “some problem,” and 3 for “extreme problem.” The utility score of 1.000 corresponds to full health state (1, 1, 1, 1, 1). The following coefficients are used to compute for utility score:

Table 7-1 Coefficients for calculating utility score

Dimension	No problem (1)	Some problem (2)	Extreme problem (3)
Mobility	0	0.069	0.314
Self-care	0	0.104	0.214
Usual activity	0	0.036	0.094
Pain / discomfort	0	0.123	0.386
Anxiety / depression	0	0.071	0.236
		Constant = 0.081	Constant = 0.269

For example, for a health state of mobility = 1, self-care = 1, usual activity = 2, pain/discomfort = 2, and anxiety/depression = 3, the utility score is 1.0 - 0.081 - 0.036 -

$0.123 - 0.236 - 0.269 = 0.255$. The worst health state (3, 3, 3, 3, 3) corresponds to utility score -0.594.

Endpoints

- Absolute change from baseline of EQ5D_{vas} score at each visit
- Absolute change from baseline of EQ5D_{utility} score at each visit

Data for Part A and B pooled for weeks 1-4 change from baseline of EQ5D_{vas} score at Week 2 and 4 will be plotted as an individual overlay plot with a mean (+/-SE) line overlaid.

Data for Part B change from baseline of EQ5D_{vas} score at each visit will be plotted as an individual overlay plot with a mean (+/-SE) line overlaid.

Data for Part A, B and C pooled for weeks 1-4 change from baseline of EQ5D_{utility} score at Week 2 and 4 will be plotted as an individual overlay plot with a mean (+/-SE) line overlaid.

Data for Part B change from baseline of EQ5D_{utility} score at each visit will be plotted as an individual overlay plot with a mean (+/-SE) line overlaid.

Data for Part C change from baseline of EQ5D_{utility} score at each visit will be plotted as an individual overlay plot with a mean (+/-SE) line overlaid.

All data for EQ5D will be listed by Part and treatment group.

8 Statistical methods for safety and tolerability data

All safety data will be listed and summarized by Part unless otherwise stated.

Disposition

Frequency counts of the number of patients completing/discontinuing from the study will be provided together with frequency count of the reason for discontinuation

Demographics

A summary of demographics will be produced containing Frequency counts of Race, Ethnicity and Sex together with summary statistics for Baseline Age, Height, Weight and BMI, and other related baseline values.

Immunogenicity

All Anti-drug antibodies will be listed by treatment, patient, visit/time, antibody Y/N, titer value. Summary statistics will be provided by treatment and visit.

Vital signs

All vital signs data will be listed by treatment, patient, and visit/time and if ranges are available abnormalities (and relevant orthostatic changes) will be flagged. Summary statistics will be provided by treatment and visit/time.

In Part C all summary tables will also be provided by age group (<18 years and ≥18 years).

ECG evaluations

All ECG data will be listed by treatment, patient and visit/time, abnormalities will be flagged. Summary statistics will be provided by treatment and visit/time.

In Part C all summary tables will also be provided by age group (<18 years and ≥18 years).

Standard clinical laboratory evaluations

All laboratory data will be listed by treatment, patient, and visit/time and abnormalities will be flagged. Summary statistics will be provided by treatment and visit/time.

In Part C all summary tables will also be provided by age group (<18 years and ≥18 years).

Additional time-profiles will be provided graphically for circulating monocytes, Creatine Kinase and ALT, AST (liver enzymes). This will be presented for Part A*, Part B* and Part C.

Special clinical laboratory evaluations

All laboratory data will be listed by treatment, patient, and visit/time and if ranges are available abnormalities will be flagged. Summary statistics will be provided by treatment and visit/time.

Adverse events

All information obtained on adverse events will be displayed by treatment and patient. The number and percentage of subjects with adverse events will be tabulated by body system and preferred term with a breakdown by treatment. An adverse event starting in one period and continuing into the next period is counted only in the onset period. A subject with multiple adverse events within a body system [within a treatment period] is only counted once towards the total of this body system.

Frequency counts will be produced for adverse events by maximum severity and the same table produced for adverse events that are related to study drug. An overall summary of the number of adverse events categorised by serious, related, leading to discontinuation and death. Summary statistics will be produced for the duration of adverse events by preferred term.

Additional listing of adverse events of special interest will also be provided. Adverse Events of special interest will be identified by medical review of the preferred terms occurring in the data in addition to periorbital edema already identified.

In Part C all summary tables will also be provided by age group (<18 years and ≥18 years).

Concomitant medications / Significant non-drug therapies

All concomitant therapies will be listed by treatment group and patient.

10 Reference list

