CL	The systemic (or total body) clearance from plasma (or serum or blood) following intravenous administration [volume / time]	
MRT	The mean residence time	
T1/2	Half life	
Tmax	The time to reach the maximum concentration after drug administration [time]	
Vss	The volume of distribution at steady state following intravenous administration [volume]	

Confidential

Glossary of terms	
Assessment	A procedure used to generate data required by the study.
Enrollment	Point/time of subject entry into the study; the point at which informed consent must be obtained (i.e., prior to starting any of the procedures described in the protocol).
Investigational drug	The study drug whose properties are being tested in the study; this definition is consistent with US CFR 21 Section 312.3 and is synonymous with "investigational new drug."
Subject number	A number assigned to each subject who enrolls in the study. When combined with the center number, a unique identifier is created for each subject in the study.
Period	A minor subdivision of the study timeline; divides phases into smaller functional segments such as screening, baseline, titration, washout, etc.
Premature subject withdrawal	Point/time when the subject exits from the study prior to the planned completion of all study drug administration and assessments; at this time all study drug administration is discontinued and no further assessments are planned.
Randomization number	A unique identifier assigned to each randomized subject, corresponding to a specific treatment arm assignment.
Stop study participation	Point/time at which the subject came in for a final evaluation visit or when study drug was discontinued whichever is later.
Study drug	Any drug administered to the subject as part of the required study procedures; includes investigational drug and any control drugs.
Study drug discontinuation	Point/time when subject permanently stops taking study drug for any reason; may or may not also be the point/time of premature subject withdrawal.
Subject	An individual who has consented to participate in this study. The term Subject may be used to describe either a healthy volunteer or a patient.
Variable	Information used in the data analysis; derived directly or indirectly from data collected using specified assessments at specified time-points.

Novartis

Confidential

Amended Protocol Version v07 (Clean) Corporate Confidential Information

Novartis

Confidential

Page 29 Protocol No. CMCS110X2201

Confidential

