3.2.3.2 Part C

Part C is a randomized, double-blind, parallel-arm adaptive dose exploration study. The goal of Part C is to identify a MCS110 dose lower than 10 mg/kg, which is as efficacious as 10 mg/kg, but may have less side effects. In order to proceed fast, two promising lower doses will be evaluated in parallel, 3 mg/kg and 5 mg/kg of MCS110. Simulations run using prior study information at week 12, log (ratio) of tumor size, and a conservative standard deviation estimate, show that 6 patients per arm in the 3 and 5 mg/kg groups will provide >80% power to declare the lower doses efficacious or not, compared to the 10 mg/kg group.

Once an efficacious lower dose will be identified either 3 mg/kg or 5 mg/kg, the identified arm may be expanded to up to approximately 10 patients for confirmation of safety and efficacy in more patients.

Rationale for assessment schedule C - Adolescent patients

The minimum body weight will be reduced to 30 kg, which is the lower range for children at the age of 12 years.

As per international guidelines for clinical trials in pediatric patients (Howie 2011), the blood volume collected at a time point from a subject 30kg body weight should must not exceed 25 mL per time point, and 50 mL in 8 weeks.

In order to comply with these recommendations only the key safety, PK, PD and Immunogenicity blood samples will be collected and analyzed (see Section 13 Appendix 1: Sample Log, Part C-Adolescent patients).

Risk assessment for effects of MCS110 on adolescent patients is described in the Section 3.5.2.

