The same model as above will also be applied to compare the efficacy of the 3 mg/kg and 5 mg/kg to the 10 mg/kg dose (instead of Placebo).

Part B and C (referenced as Part B* hereafter)

Part B includes all data from multiple dosing Parts. In Part B, treatment group 1 = MCS110 throughout the trial, treatment group 2 = Placebo for the first dose and MCS110 from the second dose. In Part C, treatment arm 1 = MCS110 3 mg/kg, treatment arm 2 = MCS110 5 mg/kg, treatment arm 3 = MCS110 10 mg/kg, for patients in treatment arms 1 and 2 that switch to 10 mg/kg after 3 doses, they will be included in their original treatment group for the first 3 doses and will added in a separate group after that (4= MCS110 3 mg/kg for 3 doses and 10 mg/kg afterwards and 5= MCS110 5 mg/kg for 3 doses and 10 mg/kg afterwards), no re-calculation of baseline will occur for the people who change treatments.

Tumor volumes will be listed at each MRI assessment timepoint till the end of the study by treatment groups.

Part B*: MCS110 data only, by including data starting from the 1st dose of MCS110 in all treatment groups of Parts B and C. More specifically, for Part B treatment group 2, the measurement right before patients receiving the first dose of MCS110 (2nd dose from screening) will be treated as the new baseline and assessment time-points will be adjusted accordingly. Summary statistics of the consolidated tumor volume for the raw values, percent change and absolute change from baseline.

Arithmetic mean (+/-) SE on percent change from baseline vs time plot will be produced for Part B*. Waterfall plot of the maximum reduction until 8 Weeks after last dose will be produced in regards of number of doses received.

Overall Time to complete tumor ablation will be summarised up to the primary endpoint (8 weeks after the last MCS110 dose), along with a summary of overall time to $\geq 50\%$, and $\geq 80\%$ ablation. The number and frequency of patients reaching each level will also be included in the summary.

Overall Time to complete ablation is the time (in weeks) - from first MCS110 dose to the first time when there is no tumor detected. Overall time to $\geq 50\%$, and $\geq 80\%$ ablation is the time from first MCS110 dose to reach maximum ablation of [50%, 80%) and [80%, complete) respectively.

Part C

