Tumor volumes will be listed and descriptively summarized at each MRI assessment time by treatment arm (treatment arm 1 = MCS110 3 mg/kg, treatment arm 2 = MCS110 5 mg/kg, treatment arm 3 = MCS110 10 mg/kg). For patients in treatment arms 1 and 2 that switch to 10 mg/kg after 3 doses, they will be treated as a separate group throughout the study (4= MCS110 3 mg/kg for 3 doses and 10 mg/kg afterwards and 5= MCS110 5 mg/kg for 3 doses and 10 mg/kg afterwards) This approach will be applied for all analyses of Part C where the treatment group is used. In addition, incidences of patients with partial response (PR), stable disease (SD) and progressive disease (PD) will be listed by treatment arm.

All summary tables (tumor volumes and response) will also be provided by age group (<18 years and ≥ 18 years).

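### Part C adverse event tables: as written, the SAP's grouping of escalated patients merges their 3 or 5 mg/kg events with later 10 mg/kg events, and no specified table gives the adverse event rate on a lower dose among all patients assigned to it

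*SAP*

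**What the plan says.** SAP Section 8 has adverse events "tabulated by body system and preferred term with a breakdown by treatment". It adds that "An adverse event starting in one period and continuing into the next period is counted only in the onset period", and that a subject with several events in a body system counts once, with the treatment period given in brackets as the unit. Protocol 9.7 carries the same counting rules. Section 8 does not list the Part C columns or say what a period is in Part C. The only definition is the generic one in the protocol glossary: "A minor subdivision of the study timeline; divides phases into smaller functional segments such as screening, baseline, titration, washout, etc".

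SAP 7.1, Part C, deals with patients who start on 3 or 5 mg/kg and move to 10 mg/kg after three doses: "they will be treated as a separate group throughout the study", numbered 4 and 5. It continues: "This approach will be applied for all analyses of Part C where the treatment group is used".

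The Part B* paragraph of the same section, which also takes in Part C, treats these patients differently: "they will be included in their original treatment group for the first 3 doses and will added in a separate group after that".

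Protocol 3.2.3.2 gives the goal of Part C as finding a dose below 10 mg/kg "which is as efficacious as 10 mg/kg, but may have less side effects". Safety and tolerability is a primary objective of Part C (Protocol 2.7).

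**The concern.** Part C is meant to show whether a lower dose is better tolerated. That needs the adverse event rate during treatment with 3 or 5 mg/kg among everyone assigned to that dose. The whole-study path grouping does not give it. An event that starts after the first 3 mg/kg infusion in a patient who later escalates falls in the 3-to-10 column, next to that patient's events on 10 mg/kg. The 3 mg/kg column loses that patient altogether.

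Membership of the low-dose columns is thus decided by what happened after randomisation. Protocol 5.5.5.2 ties escalation to two things: a week-12 volume reduction below 45%, and the drug having been tolerated. The second is closely related to the outcome being compared.

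The protocol's own expectation is affected. Section 3.5.5 does not expect periorbital edema and rash at the lower doses, while Section 3.5.1 reports periorbital swelling in 15 of 18 Part C patients, pooled over doses. Checking the expectation requires the dose at onset.

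**Working it through.** The documents give no figure to reproduce. The check is a reading of the rules together, then arithmetic on stated assumptions.

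**1. Do the rules reach the same table?** The SAP 7.1 Part C rule covers all Part C analyses that use treatment group. Section 8 breaks adverse events down by treatment, names no other columns and makes no exemption. On its wording the rule reaches these tables.

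**2. What the merged column shows.** Assume a per-patient event risk of 20% over the low-dose stage and 50% over the 10 mg/kg stage, independent.
- 3-to-10 column: 1 − (0.8 × 0.5) = 60%.
- With a low-dose risk of 10%: 1 − (0.9 × 0.5) = 55%. With 30%: 1 − (0.7 × 0.5) = 65%.

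A threefold range in the low-dose risk moves the merged figure by only 10 points, and neither stage's rate can be recovered from it.

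**3. How selection acts.** Under Protocol 5.5.9 a patient with a drug-related SAE is withdrawn, so such a patient before dose 4 stays in the low-dose column. Suppose there is one among 6 assigned (1/6 = 17%). If three others escalate, the column shows 1/3 = 33%. The bias can also go the other way: a tolerated event in a patient who later escalates leaves the low-dose column.

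**4. What share leaves the low-dose columns.** Inputs:
- Cut-off: 45% reduction, a log ratio of log(0.55) = −0.598.
- SD of the log ratio: Protocol 9.13 gives 0.2 × √2 = 0.28 and 0.3 × √2 = 0.42. These are Part A planning values; their use at week 12 is an assumption.
- All patients are taken to tolerate the drug.

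Share below the cut-off = Φ[(log(1 − r) − log(0.55)) / SD], where r is the true (median) reduction.

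| True reduction r | log(1 − r) | SD 0.28 | SD 0.42 | Of 12 planned lower-dose patients |
|---|---|---|---|---|
| 40% | −0.511 | 62% | 58% | about 7 |
| 45% | −0.598 | 50% | 50% | 6 |
| 50% | −0.693 | 37% | 41% | 4 to 5 |
| 60% | −0.916 | 13% | 23% | 2 to 3 |

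The 12 are the two planned arms of 6 (Protocol 5.2.3). The same share of their 12 × 12 = 144 patient-weeks in the low-dose stage leaves the low-dose columns.

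**5. Precision.** If an arm of 6 is left with 3, the exact two-sided 95% upper limit with no event seen goes from 1 − 0.025^(1/6) = 46% to 1 − 0.025^(1/3) = 71%. This illustrates a rare event. It does not describe periorbital swelling, which was common.

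**The case against.** The strongest reply is that the two rules answer different questions. The onset sentence settles which period an event is counted in; SAP 7.1 settles which group a patient belongs to. Path groups split before and after escalation would satisfy both. That is right, and a reader who infers that the SAP contains two contradictory attribution rules goes further than the text. But the SAP specifies no such split and does not define the period on which it would rest. Even with the split, the low-dose stage would be spread over two columns and would need adding up.

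A second reply is that the grouping rule sits in the pharmacodynamic chapter under the primary endpoint, and that Section 8 speaks of treatment for adverse events but of treatment group for concomitant therapies. Table shells are not among the documents, so the columns to be programmed cannot be checked. This leaves room for doubt, but the scope sentence is broad and nothing in Section 8 narrows it.

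Third, a reader might infer that the 3 and 5 mg/kg columns hold week-12 responders only. They hold everyone who did not escalate, including patients who stopped early and poor responders who did not tolerate the drug.

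Fourth, a reader might infer that the dose comparison is lost. It is not: Section 8 displays all adverse event information by treatment and patient, and start dates are collected (Protocol 7.1), so dose at onset can be rebuilt by hand for about 15 to 19 patients. That is a remedy after the fact, not a planned comparison.

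Finally, the size depends on an unknown effect. Part B averaged about a 50% reduction after three doses of 10 mg/kg (Protocol 1.4); if a lower dose matched that, 37-41% would leave. This stands, which is why a range is given.

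**Conclusion.** The point holds as a gap in the specified tables. Applied as written, SAP 7.1 Part C merges two dose stages in the 3-to-10 and 5-to-10 columns and leaves the 3 and 5 mg/kg columns selected on response and tolerability. No specified table then gives the adverse event rate on a lower dose among all patients assigned to it, on a primary objective. The Part B* paragraph makes the inconsistency visible, since it keeps the first three doses of the same patients in their original group. Section 8 asks for monocyte, CK, ALT and AST profiles under both Part B* and Part C, so the same early data would appear under two groupings.

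The share leaving the low-dose columns ranges from about 37-41% (true reduction 50%) to 58-62% (40%), given the Part A SDs, no tolerability stops and a low-dose effect that is not known; at a true 60% it would be 13-23%. The direction of the resulting bias depends on the type of event. The documents do not support calling this a contradiction or an irrecoverable loss. It should be corrected before database lock.

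**What to change.** In SAP Section 8, for Part C:

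- **Before dose 4.** Tabulate events with onset from dose 1 to before dose 4 by initially assigned dose, in all dosed patients. For patients who never receive dose 4, end the window at a stated cut-off. Include open-label extension patients and identify them.
- **From dose 4.** Tabulate events by the dose being given at onset, keeping 10 mg/kg after 3 or 5 mg/kg apart from 10 mg/kg from the start. Assign follow-up events to the last dose received, and show events during re-dosing separately.
- **Scope.** State that these tables are exempt from the whole-study grouping in SAP 7.1 Part C, define the two periods, and keep the path groups as a supplementary table.

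The cost is SAP wording and a dose-at-onset flag derived from dosing and event dates already collected. The downside is a few more columns, with small numbers after dose 4. No change to trial conduct is needed.
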